2. STUDY PROTOCOL

This was a prospective clinical study to be conducted at multiple clinical sites located in the United States. This clinical device study assessed the substantial equivalence of NIDEK TONOREF III to a predicate devices regarding tonometry and pachymetry.

Three sets of devices

were used. The device order of measurements captured on the predicate and investigational devices were randomized. This was an open-label study, meaning all study staff and subjects

were aware of which devices were being used. However, the investigators were blinded to the results obtained by each device, to protect against observer bias.

Eligible subjects were measured by all study devices and the safety of the devices were also assessed. The study period was one day.

3. STATISTICAL ANALYSIS PLAN

The mean IOP value measured with the NIDEK TONOREF III minus the IOP value measured with the predicate tonometer (GAT) equals the difference between the test and predicate tonometer.

Descriptive statistics, including mean and standard deviation of the differences between the test device and the GAT, Bland and Altman plot and linear regression were analyzed. The first qualified eyes in each pressure range only will be used for the above analysis

The mean corneal thickness values measured with minus the corneal thickness value measured with the predicate pachymeter equals the difference between the test and predicate pachymeter.

Descriptive statistics, including mean difference and standard deviation of the differences between the test device and the Bland and Altman plot and Deming regression were analyzed.

Any sight threatening adverse event associated with the TONOREF III or the predicate devices including subject complaints and clinical observations were collected.

The data analysis included a comparison of the frequencies of all adverse events and adverse device effects. Adverse events reported were listed by subject and subject complaints and corneal abrasions for the test and reference devices were specified.

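### Does the plan need a stated number of eyes per subject for the IOP and corneal thickness comparisons?

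*Combined protocol and SAP*

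**What the plan says.** Section 2 (Study Protocol) describes measurement by person: "Eligible subjects were measured by all study devices". It does not say whether one or both eyes were measured.

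Section 3 (Statistical Analysis Plan) defines the IOP difference as TONOREF III minus GAT. It lists the mean and SD of the differences, a Bland-Altman plot and a linear regression, and closes with the only eye rule in the text: "The first qualified eyes in each pressure range only will be used for the above analysis".

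The corneal thickness paragraphs come next. The subtraction "equals the difference between the test and predicate pachymeter", and the analysis is again descriptive: "Bland and Altman plot and Deming regression were analyzed". No eye rule is attached. Safety is reported by person: "Adverse events reported were listed by subject".

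Neither section gives a sample size, confidence interval, hypothesis test, equivalence margin or between-eye correlation.

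**The concern.** The eye rule can be read in two ways. It may mean each subject's first qualifying eye, sorted into pressure ranges. It may also mean the first eyes to qualify until a range is filled, and then nothing prevents both eyes of one person from entering, in the same range or in different ones. The rule also looks back to the IOP analysis only, so the pachymetry comparison has no stated unit of analysis.

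Fellow eyes share anatomy and measurement conditions, so their device differences are likely to be correlated. If pairs were treated as independent observations, standard errors would be too small, and any interval for the bias, the limits of agreement or the regression coefficients would be too narrow. Because the study supports a claim of substantial equivalence, overstated precision would matter.

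**Working it through.** **What the text settles.** The documents give no figure to reproduce, so the first check is textual.

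- The IOP rule mentions eyes and pressure ranges but not eyes per subject. Both readings are open, and one of them selects by subject.
- The pachymetry paragraphs are silent on the unit of analysis.
- Measuring subjects with every device is compatible with one eye or two.
- Listing adverse events by subject is normal practice and does not bear on the unit of the agreement analysis.
- Surplus eyes in a pressure range could come from surplus subjects as easily as from fellow eyes.

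**Inputs for the size of the effect (all assumed).** Let n be the number of analysed eyes, p the share of them that come in pairs, ρ the between-eye correlation of the device differences, and σ² their variance.

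**Effect on the listed outputs.**

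- Mean difference: each eye has the same expected difference whether or not its fellow is included, so the mean is unbiased.
- SD of differences: the n eyes contain np/2 pairs, each adding 2ρσ² to the variance of the sum. Hence Var(mean) = (σ²/n)(1 + pρ), and E(s²) = [nσ² − σ²(1 + pρ)]/(n − 1) = σ²[1 − pρ/(n − 1)]. With n = 200, p = 1 and ρ = 0.7, √(1 − 0.7/199) = 0.998, so the SD is about 0.2% low.
- Bland-Altman plot: it is drawn from that mean and SD, so it is essentially unchanged.
- Regression: what has been shown for pairing is a change in the precision of the slope, not a shift in the fitted line.

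**Effect on intervals, if any were reported by one-level methods.**

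- True over naive SE of the mean: √(1 + pρ).
- Coverage of a nominal 95% interval: 2Φ(1.96/√(1 + pρ)) − 1.
- True over naive SE of a limit of agreement: √{[(1 + pρ) + 1.92(1 + pρ²)]/2.92}, where 1.92 = 1.96²/2.

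| p | ρ | SE ratio, mean | Coverage | SE ratio, limit of agreement |
|---|---|---|---|---|
| 0 | any | 1.00 | 95% | 1.00 |
| 0.5 | 0.3 | 1.07 | 93% | 1.04 |
| 0.5 | 0.5 | 1.12 | 92% | 1.08 |
| 0.5 | 0.7 | 1.16 | 91% | 1.13 |
| 1 | 0.3 | 1.14 | 91% | 1.08 |
| 1 | 0.5 | 1.22 | 89% | 1.16 |
| 1 | 0.7 | 1.30 | 87% | 1.25 |

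Coverage drops below 93% once pρ exceeds (1.96/1.812)² − 1 = 0.17, where 1.812 is the two-sided 93% normal quantile.

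**What has to be true for harm.** Both eyes must have been measured, both must have been analysed, their differences must be positively correlated, an interval must be reported, and it must be computed as though the eyes were independent. The documents support none of these except by silence. They give no basis for placing the study at any row of the table, including the first.

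**The case for a change.** The strongest case for a change is that a plan should determine its own analysis set. Under the two readings of the IOP rule, two analysts could build different sets from the same data. Pachymetry is the firmer half of the complaint: pressure ranges are an IOP concept, so even a generous reading of the rule does not carry over to corneal thickness. A submission arguing substantial equivalence may well report intervals, and one or two sentences would close the question.

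Part of this stands. The available text does not state eyes per subject for either comparison, and a report should say which eyes were used. If two eyes per subject were analysed and intervals are given, those intervals should treat the subject as the cluster.

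The rest does not carry as far as a change to the plan:

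- The two readings differ in information only if correlated fellow eyes actually enter.
- The outputs the plan commits to are nearly insensitive to the answer.
- The text is written largely in the past tense, so naming an eye in advance, or recruiting differently, may no longer be possible.
- The silence is not wholly attributable to the plan. The pachymetry sentences have visible gaps where device names seem to have been removed, and the eye-rule sentence ends without a full stop. The gaps do not look like a missing eye rule, but a lost qualifier cannot be excluded.

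**Conclusion.** No change follows. The plan leaves a detail unstated; it does not prescribe a wrong analysis. Followed as written, it yields an unbiased mean difference, an SD at most about 0.2% low (assuming 200 eyes, all paired, ρ = 0.7) and a Bland-Altman plot that is essentially the same under either reading.

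The larger figures, an SE understated by a factor of up to 1.30 and coverage down to 87%, apply only to intervals the plan does not list, and only with complete pairing, ρ = 0.7 and one-level methods. All three are assumptions, and the range that includes them also includes no effect.

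An analyst building these sets would have to settle which eyes enter, and would ordinarily either take one eye per subject or allow for the pairing. Stating that choice when the results are reported is enough. The conclusion would need another look if the results turned out to rest on intervals computed from two eyes per subject as though they were independent.

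### Read literally, the adverse-event collection rule is narrower than the planned analysis of every adverse event, and the two scopes need to be made to match

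*Combined protocol and SAP*

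**What the plan says.** Safety is covered in three sentences of section 3 (Statistical Analysis Plan) and one sentence of section 2 (Study Protocol).

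- Collection, section 3: "Any sight threatening adverse event associated with the TONOREF III or the predicate devices including subject complaints and clinical observations were collected".
- Analysis, section 3: "The data analysis included a comparison of the frequencies of all adverse events and adverse device effects".
- Listing, section 3: "Adverse events reported were listed by subject and subject complaints and corneal abrasions for the test and reference devices were specified".
- Study Protocol, section 2: "Eligible subjects were measured by all study devices and the safety of the devices were also assessed". This says that safety was looked at, but not which events were to be recorded.

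No other sentence in the available text sets a rule for collecting adverse events. Section 2 also states: "The study period was one day".

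**The concern.** The collection sentence attaches two limits to an adverse event: that it threatens sight, and that it is associated with one of the devices. The analysis sentence drops both. An analysis cannot recover events that were screened out when data were recorded, so a site that followed the collection sentence to the letter would supply fewer events than the analysis claims to count.

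The stake is how the safety comparison may be read. For an event that was neither a complaint nor an abrasion, and that was not sight-threatening or not blamed on a device, a reader could not tell whether its absence means that it did not occur or that nobody was asked to record it. The second limit adds a difficulty. Every subject was measured on all devices, and staff and subjects knew which device was in use. Under the literal rule, somebody would have to judge device association before an event entered the record at all. That is a reason to record association as an attribute of each event; it is not evidence of bias.

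**Working it through.** No formula applies, and the plan gives no safety figure to reproduce. The check is a comparison of scopes.

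**Step 1: the sentences side by side.**

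| Sentence | Limited to sight-threatening? | Limited to device-associated? |
|---|---|---|
| Collection (section 3) | Yes | Yes |
| Analysis, adverse events (section 3) | No | No |
| Analysis, adverse device effects (section 3) | No | Yes, by its nature |
| Listing by subject (section 3) | No | No |
| Complaints and abrasions by device (section 3) | No | Reported per device |
| Safety statement (section 2) | No scope given | No scope given |

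The term adverse event (singular or plural) occurs 3 times, all in section 3. One occurrence (collection) carries both limits, and 3 − 1 = 2 (analysis and listing) carry neither. These are counts of wording, not of events.

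**Step 2: what the literal rule covers.** Classify events by two yes/no attributes, sight-threatening and device-associated, giving 2 × 2 = 4 classes. The literal rule collects the one class where both answers are yes. The analysis, read at face value, covers all 4. The remaining 4 − 1 = 3 classes are inside the analysis and outside the literal collection rule:

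- sight-threatening but not associated with a device;
- associated with a device but not sight-threatening;
- neither.

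This says nothing about how many events fall in each class.

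**Step 3: a check on internal sense.** The analysis sentence treats adverse events and adverse device effects as two categories. The documents do not define the second. On the ordinary meaning, an event attributed to a device, a rule that collects only device-associated events leaves little to distinguish the two. The literal rule therefore sits badly with the analysis on a second count.

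**Step 4: what the rest of the text recovers.** The listing sentence says that complaints and corneal abrasions were specified for the test and reference devices. The collection sentence itself names complaints and clinical observations, and an abrasion is naturally a clinical observation. These two categories were therefore probably captured whatever their severity. What remains open is the rest of the three classes in step 2.

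**Step 5: the two ways to read the analysis sentence.**

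- If all is meant at face value and collection was literal, the frequencies omit whatever occurred in the open classes.
- If all means all those collected, the arithmetic is consistent but the label claims more than was recorded.

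Only if collection was in fact unrestricted is nothing missing, and then the two limits in the collection sentence are simply wrong.

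**The case against.** The best case on the other side is that context favours the broad reading. Complaints and observations do not usually threaten sight, so naming them suggests a list of things collected rather than one restricted class. The sentence joins a singular subject to a plural verb, which points to loose drafting. It also lacks the word *only*, which the same section does use when it restricts the eyes analysed: "The first qualified eyes in each pressure range only will be used for the above analysis". *Reported* in the listing sentence, and *all* in the analysis sentence, can both be read as referring to what was collected. The study period was a single day, which leaves limited room for unrelated events. Finally, one part of the document was removed before review and could hold a fuller definition.

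Much of this stands. It defeats a stronger reading that someone might infer: that complaints and corneal abrasions went unrecorded because abrasions are not named in the collection sentence. The documents do not support that, for the reasons in step 4 of the working. The lack of the word is a fact about vocabulary, not about scope.

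It does not remove the point. The phrase about complaints and observations can equally list members of the already limited set, and the text does not say which was meant. If the broad reading is right, the two limits mislead and should go. Reading *all* as all those collected leaves a filtered count under an unfiltered label. No gap is visible inside the safety sentences, so redaction does not explain the mismatch.

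**Conclusion.** The point holds as a minor internal inconsistency: a stated collection rule and a stated analysis do not have the same scope, and nothing in the available text reconciles them.

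Its size cannot be estimated, since the documents give no event rate, event count or sample size. The effect runs from none, if collection was unrestricted, to an undercount of unknown size among events other than complaints and abrasions, if the rule was applied literally.

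A reader might infer that adverse events were missed. The documents do not show this: they describe wording, not what sites did. Nor does the point reach the intraocular pressure or corneal thickness agreement analyses, which do not use adverse-event data.

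The conclusion assumes that the visible safety sentences are the operative ones and that no fuller definition exists elsewhere.

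**What to change.** Make the two scopes match. The choice depends on what was actually captured.

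- **If all events were captured:** delete the sight-threatening and device-association limits from the collection sentence, and treat severity and device relationship as attributes recorded for each event. This is a wording change that needs no new data.
- **If capture was narrower:** replace the reference to all adverse events in the analysis sentence, and in any safety conclusion, with the scope actually captured. The cost is a narrower safety statement.
- **If any collection is still to occur:** collect every adverse event regardless of severity or presumed device relationship, and record both attributes. The cost is slightly more events to record. This route is secondary, because every safety verb is in the past tense. It is kept because the tenses elsewhere are mixed, as in "This was a prospective clinical study to be conducted at multiple clinical sites located in the United States".
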